### **7.2.2.1 Blood Volume**

The total amount of blood collected from each subject over the duration of the study, including any extra assessments that may be required, will not exceed 450 mL.

### **7.2.2.2 Laboratory Specimen Preparation, Handling, and Storage**

Instructions related to handling of safety laboratory samples and PK blood samples, including how to process blood and prepare aliquots, sample storage, and disposition are provided in the MOP.

A hypersensitivity sample will be collected on all subjects at baseline (pre-dose on Day 1) and stored frozen on site. If a subject experiences anaphylaxis or an anaphylactoid event related to the infusion, three additional samples will be collected during onset, 2 or more hours after onset and after resolution of symptoms. Samples will only be analyzed in the event of a hypersensitivity reaction. Hypersensitivity samples will be collected, processed and stored frozen on site and sent to the testing lab if needed. Baseline samples will be discarded at the end of the study if there are no hypersensitivity events. Prior to discarding samples, DMID or an authorized representative must notify the site and approve sample destruction.

Details on the collection, storage, testing, and disposition of used and unused hypersensitivity samples will be provided in the protocol-specific MOP.

### **7.2.2.3 Laboratory Specimen Shipping**

Specimen shipment will occur at intervals during this study following all applicable International Air Transport Association requirements and according to the specifics for storage temperature and documentation as detailed in the central (clinical) laboratory manual and MOP as appropriate.

Further instructions for specimen shipment are included in the MOP, as appropriate.

Clinical laboratory assessments will be performed by the clinical site CLIA approved laboratories indicated on the Form FDA 1572. Plasma samples for PK analyses and ADA will be shipped on dry ice to Fisher BioServices before sending them to Aptuit (Verona) Srl.

## 8 ASSESSMENT OF SAFETY

### 8.1 Assessing and Recording Safety Parameters

Safety will be assessed through the evaluation of AEs, vital signs, ECGs, and conventional clinical laboratory data (clinical chemistry panels and hematology, coagulation, immunogenicity, and urinalysis evaluations), according to the Schedule of Events ([Appendix A](#)).

#### 8.1.1 Adverse Events

International Council for Harmonisation E6 defines an AE as any untoward medical occurrence in a patient or clinical investigation subject administered a pharmaceutical product regardless of its causal relationship to the study treatment. The FDA defines an AE as any untoward medical occurrence associated with the use of a drug in humans, whether or not considered drug related. A treatment-emergent AE (TEAE) is defined as an AE that occurs during or after the first study product infusion and up through the final visit. Only TEAEs will be documented as AEs in this study. Adverse events that occur between the time of consent and administration of study product will be recorded in the medical history.

An AE can therefore be any unfavorable and unintended sign (including a CS abnormal laboratory finding), symptom, or disease temporally associated with the use of a medicinal (investigational) product. The occurrence of an AE may come to the attention of study personnel during study visits and interviews of a study recipient presenting for medical care, or upon review by a study monitor.

All AEs will be captured on the appropriate data collection form and eCRF. Information to be collected for AEs includes event description, date of onset, assessment of severity, relationship to study product and alternate etiology (assessed only by those with the training and authority to make a diagnosis and listed on the Form FDA 1572 as an investigator), date of resolution, seriousness, and outcome. Adverse events occurring during the study collection and reporting period will be documented appropriately regardless of relationship. Adverse events will be followed through resolution or stabilization, as indicated by an investigator.

Any medical condition that is present at the time that the subject is screened will be considered as baseline and not reported as an AE. However, if the severity of any pre-existing medical condition increases, it should be recorded as an AE.

---

Medically-indicated laboratory tests (emergency or unscheduled tests) should be conducted at the local site laboratory.

The site investigator should employ the best medical judgment in determining how to manage AEs and SAEs.

### **8.1.1.1 Adverse Events Grading**

All AEs (laboratory and clinical symptoms) will be graded by the licensed study physicians on Form FDA 1572 for severity and assessed for relationship to study product. The start and stop date of each reported AE will be recorded on the appropriate data collection form and eCRF.

#### **Severity of Event:**

Subjects who screened and enrolled prior to Protocol Version 11.0, AEs will be assessed by the investigator using a protocol-defined grading system (see Toxicity Table, [Appendix B](#)). For events not included in the protocol-defined grading system, the following guidelines will be used to determine severity:

- **Mild (Grade 1):** Events that are usually transient and may require only minimal or no treatment or therapeutic intervention and generally do not interfere with the subject's usual activities of daily living.
- **Moderate (Grade 2):** Events that are usually alleviated with additional specific therapeutic intervention. The event interferes with usual activities of daily living, causing discomfort but poses no significant or permanent risk of harm to the research participant.
- **Severe (Grade 3):** Events interrupt usual activities of daily living, or significantly affect clinical status, may require intensive therapeutic intervention, or death related to an AE. Severe events are usually incapacitating.

Subjects who screen and enroll with Protocol Version 11.0, AEs will be assessed by the investigator using the NCI CTCAE, Version 5.0 – November 2017. For events not included in the NCI CTCAE grading system, the following guidelines will be used to determine severity:

- Grade 1 (Mild): Asymptomatic or mild symptoms; clinical or diagnostic observations only; intervention not indicated.

---

- Grade 2 (Moderate): Minimal, local, or noninvasive intervention indicated; limits age-appropriate instrumental activities of daily living (eg, preparing meals, shopping for groceries or clothes, using the telephone, managing money).
- Grade 3 (Severe): Medically significant but not immediately life-threatening; hospitalization or prolongation of hospitalization indicated; disabling; limits self-care activities of daily living (eg, bathing, dressing and undressing, feeding self, using the toilet, taking medications, and not bedridden).
- Grade 4 (Life threatening): Urgent intervention indicated.
- Grade 5 (Death).

**Relationship to Study Product:** The assessment of the AE's relationship to study product will be done by the licensed study physician indicated on the Form FDA 1572 and the assessment will be part of the documentation process. Whether the AE is related or not is not a factor in determining what is or is not reported in this study. If there is any doubt as to whether a clinical observation is an AE, the event should be reported.

In a clinical study, the study product must always be suspect. The relationship to study product will be assessed for AEs using the terms "Related" and "Not Related".

- An investigator should use good clinical judgment. If the event is believed to be unrelated to study product, an alternative plausible explanation must be provided. Otherwise, AEs will be considered related to the study product.

### 8.1.2 Serious Adverse Events

An AE or suspected adverse reaction is considered an SAE if it occurs between the time of receiving study medication and the final study visit, and in the view of either the site PI or sponsor; it results in any of the following outcomes:

- Death,
- A life-threatening\* AE,
- Inpatient hospitalization or prolongation of existing hospitalization,
- A persistent or significant incapacity or substantial disruption of the ability to conduct normal life functions, or

---

- A congenital anomaly/birth defect.
- Important medical events that may not result in death, be life-threatening, or require hospitalizations may be considered serious when, based upon appropriate medical judgment, they may jeopardize the patient or subject and may require medical or surgical intervention to prevent one of the outcomes listed in this definition. Examples of such medical events include allergic bronchospasm requiring intensive treatment in an emergency room or at home, blood dyscrasias, or convulsions that do not result in inpatient hospitalization, or the development of drug dependency or drug abuse.

\*Life-threatening AE: An AE is considered “life-threatening” if, in the view of either the site PI or sponsor, its occurrence places the patient or subject at immediate risk of death. It does not include an AE that, had it occurred in a more severe form, might have caused death.

SAEs will be:

- Assessed for severity and relationship to study product and alternate etiology (if not related to study product) by a licensed study physician listed on the Form FDA 1572 or by the Institution as the site PI or sub-investigator.
- Recorded on the appropriate SAE data collection form and eCRF.
- Followed through resolution by a licensed study physician (for IND studies, a physician listed on the Form FDA 1572 as the site PI or sub-investigator).
- Reviewed and evaluated by DMID or SMC (periodic review unless related), and the IRB/IEC.

### **8.1.3. Suspected Unexpected Serious Adverse Reactions (SUSAR)**

A SUSAR is any SAE where a causal relationship with the study product is at least reasonably possible but is not listed in the IB, Package Insert, and/or Summary of Product Characteristics.

The IND Sponsor is responsible for making the determination of which SAEs are “serious and unexpected suspected adverse reactions” (SUSARs) as defined in 21 CFR 312.32.

- *Suspected Adverse Reaction* means any AE for which there is a reasonable possibility that the drug caused the AE.
- *Unexpected Adverse Event* means an AE that is not listed at the specificity or severity that has been observed.

---

All SUSARs (as determined by the IND Sponsor) will be reported to the FDA as IND Safety Reports per 21 CFR 312.32 as soon as possible but not exceeding 7 calendar days for unexpected fatal or life-threatening events, and not exceeding 15 calendar days for other qualifying events. IND Safety Reports will also be provided to the IRB.

#### **8.1.4 Unanticipated Problem**

An Unanticipated Problem (UP) is defined as any incident, experience, or outcome that meets all the following criteria:

- Unexpected (in terms of nature, severity, or frequency) given (a) the research procedures that are described in the protocol-related documents, such as the IRB approved research protocol and informed consent document; and (b) the characteristics of the subject population being studied; and
- Related or possibly related to participation in the research (possibly related means there is a reasonable possibility that the incident, experience, or outcome may have been caused by the procedures involved in the research); and
- Suggests that the research places subjects, or others (which may include research staff, family members or other individuals not directly participating in the research) at a greater risk of harm (including physical, psychological, economic, or social harm) related to the research than was previously known or expected.
- A UP must be reported within 7 calendar days of an investigator becoming aware of the actual or suspected UP.

#### **8.2 Specification of Safety Parameters**

Safety will be assessed by the frequency and severity of AEs and SAEs; the incidence and maximum intensity of AEs and SAEs, vital sign measurements, ECG findings, and clinically important changes in clinical laboratory values, defined as a change to a higher grade relative to baseline.

AEs and SAEs will be addressed as they are reported or identified by a staff member. Safety laboratory reports are reviewed as available, generally within 24 hours of sample collection.

### **8.2.1      Solicited Events**

Solicited events are AEs that are common and known to occur following administration of study product. There are no solicited events for this study.

### **8.2.2      Unsolicited Events**

Unsolicited events are any other AEs that occur following infusion of study product.

## **8.3      Reporting Procedures**

### **8.3.1      Reporting Serious Adverse Events**

Serious AEs will be followed until resolution even if this extends beyond the study reporting period. Resolution of an AE is defined as the return to pretreatment status or stabilization of the condition with the expectation that it will remain chronic.

**Any AE that meets a protocol-defined serious criterion must be submitted immediately (within 24 hours of site awareness) on a DMID SAE form to the DMID Pharmacovigilance Group, at the following address:**

### **8.3.2 Regulatory Reporting for Studies Conducted Under DMID-Sponsored IND**

Following notification from the site PI or appropriate sub-investigator, DMID, as the IND Sponsor, will report any suspected unexpected SAE. DMID will report an AE as a suspected unexpected AE only if there is evidence to suggest a causal relationship between the study intervention and the AE. DMID will submit an IND safety report to the FDA and will notify all participating site PIs (ie, all PIs to whom the sponsor is providing drug under its IND[s] or under any PI's IND[s] of potential serious risks from clinical studies or any other source, as soon as possible). DMID will report to the FDA any unexpected fatal or life-threatening suspected adverse reaction as soon as possible, but in no case later than 7 calendar days after the sponsor's initial receipt of the information. If the event is not fatal or life-threatening the IND safety report will be submitted within 15 calendar days after the sponsor determines that the information qualifies for reporting as specified in 21 CFR Part 312.32. Relevant follow-up information to an IND safety report will be submitted as soon as the information is available. Upon request from the FDA, DMID will submit to the FDA any additional data or information that the agency deems necessary, as soon as possible, but in no case later than 15 calendar days after receiving the request.

All SAEs designated as "not related" to study product(s), will be reported to the FDA at least annually in a summary format.

### **8.3.3 Reporting of Pregnancy**

Females of childbearing potential are excluded from this study unless they consent to adequate contraception.

---

Female subjects, and female partners of male subjects, must be instructed to inform the investigator immediately if they become pregnant during the study. In the event of a confirmed pregnancy or positive pregnancy test, the following actions should be taken:

- Pregnancy should be reported to Emmes within 24 hours of notification, using the applicable pregnancy report form.
- Investigator should counsel the subject regarding the possible effects of prior SAR440894 exposure on the fetus and the need to inform the study site of the outcome of the pregnancy.
- Subject should be followed, if possible, until the immediate postnatal period (6 weeks) or until termination or loss of the pregnancy. The outcome should be reported to the Medical Monitor using the Pregnancy Outcome or Abnormal Pregnancy Outcome form.

Pregnancy is not an AE itself. However, any pregnancy complication or elective termination of a pregnancy for medical reasons will be recorded as an AE or SAE. A spontaneous abortion is always considered an SAE and will be reported as described in the AE and SAE sections. Furthermore, any SAE occurring as an adverse pregnancy outcome post-study must be reported to the sponsor/DMID.

## **8.4 Type and Duration of Follow-up of Subjects After Adverse Events**

AEs and SAEs will be followed through resolution or stabilization, as indicated by an investigator.

Resolution of an AE is defined as the return to pretreatment status or stabilization of the condition with the expectation that it will remain chronic.

## **8.5 Procedures to be Followed in the Event of Abnormal Laboratory Test Values or Abnormal Clinical Findings**

The site principal investigator or sub-investigator is responsible for recording all AE/SAEs that are observed or reported during this trial, regardless of the relationship to study product. AE/SAEs, abnormal CS laboratory test values, or abnormal clinical findings will be collected, assessed, documented, and followed appropriately. Subjects who screened and enrolled prior to Protocol Version 11.0, grading of the ECG AEs will be based on the [Appendix B](#) toxicity table

---

and grading of the laboratory and vital signs AEs will be based on the [Appendix C](#) and [Appendix D](#). Subjects who screen and enroll with Protocol Version 11.0, toxicity will be assessed with the NCI CTCAE, Version 5.0 – November 2017.[4](#)

Isolated laboratory test abnormalities should not be recorded as AEs or SAEs; eg, if the laboratory abnormality is part of a clinical condition or syndrome, it should be recorded as the syndrome or diagnosis rather than as the individual laboratory abnormality. In addition, CS laboratory abnormalities or other abnormal test assessments (eg, ECGs) that are associated with signs or symptoms must be recorded as AEs or SAEs if they meet the definition of an AE (or SAE) as described in [Section 8.1](#). Clinically significant laboratory test abnormalities are documented on the laboratory form and not recorded as a separate AE eCRF but the relationship, clinical significance and grade are noted on the laboratory screen.

The site is utilizing standard panels for this protocol therefore if there are laboratory parameters not solicited in this protocol but are part of a standard panel that are abnormal and CS as determined by the site PI then the abnormal parameter will be reported on the AE eCRF.

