### Nonclinical Pharmacology and Toxicology

The safety of SAR440894 has been studied in in vivo toxicity studies including repeat dose studies (3 doses with a week interval between doses followed by a 5-week recovery period) in CD1 mice and non-human primates (NHPs), and the target organ identified was the kidney in CD1 mice.

Test article-related changes consisting of adverse renal tubular and interstitial inflammation (not dose-related in terms of incidence or severity) were seen in mice, at all doses tested, sacrificed 1 week after the last dose and were still present after 5 weeks of a recovery period. Therefore, a no observed adverse effect level (NOAEL) in CD1 mice was not identified.

In order to explore the etiology of these observations, two complementary studies were performed that included an assessment of off-target binding of SAR440894 on kidney samples from WT CD1 mice by IHC, and evaluation of immune reaction directed against SAR440894 and the formation of immune complexes. Both investigations were negative.

---

Based on the low incidence of findings in all mouse treatment groups, their lack of a clear dose/exposure-related trend in terms of incidence/severity, and the preserved functionality of the organ (no increases in blood urea nitrogen and creatinine levels), these findings are considered doubtful. In addition, this finding (test article-related changes consisting of adverse renal tubular and interstitial inflammation) can be strictly monitored in humans by evaluating blood and urine markers of renal function and injury.

There were no renal microscopic changes in the NHPs. However, mild to moderate, not dose-related, and transient increases in urine albumin/creatinine ratio and/or total protein/creatinine ratio were observed in the majority of males at the end of treatment. Based on the absence of a dose relationship, the presence in males only (despite no sex-related differences in terms of exposure), no decrease in serum albumin concentration, and no morphological changes, glomerular damage was ruled out. None of the findings were considered adverse, and the NOAEL was considered to be the top dose of 45 mg/kg, with a Day 15 mean area underneath the plasma concentration versus time curve from time 0 to the last quantifiable concentration (AUClast) of 159,000 µg·h/mL and 153,000 µg·h/mL for males and females, respectively.

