### **8.6.2      Cohort Dose-Escalation Halting Rules (Dosing through Day 14)**

- One subject has an SAE that is determined to be **related** to the study product.

OR

- Two or more subjects in a cohort experience Grade 2 or higher **related** AE (laboratory or systemic) that is coded in the same high level group term (HLGT) per MedDRA classification.

If the predefined criteria for dose escalation halting are met, the SMC will review the study data and provide guidance on how to proceed.

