### **8.6.3 Study Halting Criteria**

- One subject has an SAE that is determined to be **related** to study product.
- OR
- Three or more subjects in the study (cumulative among all cohorts) experience a Grade 3 **related** AE (laboratory or systemic) that is coded in the same HLTG per MedDRA classification.

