## **15. SUMMARY OF CHANGES IN THE CONDUCT OF THE STUDY OR PLANNED ANALYSES**

The following changes will be made in the final analysis:

- Protocol v11.0 states that creatinine clearance will be calculated and reported. However, in discussion with the study team, it was decided this parameter did not need to be included in the analysis and summaries, since eGFR is being collected and reported.
- Protocol v11.0 states that only CS abnormal laboratory findings will be reported as AEs. In discussion with the study team, it was decided related abnormal laboratory findings of any clinical significance will also be reported as AEs.

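### Protocol 8.5 contradicts 8.1.1 and 8.6 on whether an isolated laboratory abnormality is an AE, so the automatic halting rules may miss asymptomatic laboratory signals in subjects enrolled under v11.0

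*Protocol*

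**What the plan says.** **Recording (Protocol 8.5).** "Isolated laboratory test abnormalities should not be recorded as AEs or SAEs". Clinically significant (CS) abnormalities linked to signs or symptoms are to be recorded as AEs. Otherwise "Clinically significant laboratory test abnormalities are documented on the laboratory form and not recorded as a separate AE eCRF", although "the relationship, clinical significance and grade are noted on the laboratory screen". A CS abnormality in a panel parameter that the protocol did not ask for does go on the AE eCRF.

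**Definition (Protocol 8.1.1).** An AE is any unfavourable sign, "including a CS abnormal laboratory finding". No symptom is required, and every AE is to be captured on a data collection form and eCRF.

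**Halting (Protocol 8.6.1 to 8.6.3).** All three sections name laboratory AEs.
- The sentinel rule needs one related AE of Grade 3 or higher that does not resolve in time. It has no coding condition.
- The cohort rule needs two or more subjects with a related Grade 2 or higher "AE (laboratory or systemic) that is coded in the same high level group term (HLGT) per MedDRA classification".
- The study rule needs three or more subjects with a related Grade 3 "AE (laboratory or systemic) that is coded in the same HLTG per MedDRA classification" (the abbreviation is transposed in the protocol).

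**Coding (Protocol 10.5.1.1).** MedDRA coding is stated for adverse events.

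**SAP 6.7 and 15.** Before v11.0 every abnormal laboratory finding was an AE. The SAP reads v11.0 as limiting this to CS findings, then adds that "related abnormal laboratory findings of any clinical significance will also be reported as AEs". Section 15 places that decision among changes made in the final analysis.

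**The concern.** This is a first-in-human trial. The kidney was the target organ in mice and no mouse NOAEL was found. Blood urea nitrogen and creatinine did not rise in mice, and the monkey renal findings were urinary only. Protocol 2.1 answers the risk by saying that it "can be strictly monitored in humans by evaluating blood and urine markers of renal function and injury". The signal the protocol relies on is therefore a laboratory change, quite possibly without symptoms.

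Under Section 8.6, suspension at all sites and assessment by the Safety Monitoring Committee (SMC) are mandatory only when a rule is met. The data coordinating centre (SDCC) documents whether one was met through Day 14. If none was, the medical monitor approves the next cohort. If 8.5 removes asymptomatic laboratory results from the set of AEs, that objective check can report that no rule was met while the laboratory data show what the rule was written to catch. Two sites, or a site and the SDCC, could also apply the same text and reach different counts.

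**Working it through.** The plan gives no operating characteristic for the halting rules, so there is no figure to reproduce. The check is first textual, then illustrative.

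**Step 1: classify the same result under each text.** Take a post-dose abnormality of a protocol laboratory test that is graded, judged related, and asymptomatic.

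| Source | Judged CS | Judged not CS |
|---|---|---|
| Protocol 8.5, literal | Laboratory form, no AE eCRF | Not an AE |
| Protocol 8.1.1 | AE | Not named as an AE |
| SAP 6.7 and 15, v11.0 subjects | AE | AE |
| SAP 6.7, subjects before v11.0 | AE | AE |

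The three texts that bear on v11.0 subjects give three different AE sets. Section 8.5 splits the grading scale by protocol version but does not split the recording rule.

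**Step 2: look for a link from the laboratory form to the count.** The laboratory form holds relationship, significance and grade. It is not said to hold a MedDRA term. The SAP shells point the same way:
- the AE listings (for example Table 52 and Listing 13) have an HLGT column;
- the abnormal-laboratory listing (Table 62) has severity, significance and relationship but no MedDRA column;
- Tables 40 and 41 take CS and non-CS laboratory abnormalities from the laboratory results eCRFs, and AE-related discontinuation and early termination from the AE eCRF.

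Neither document says that laboratory-form entries are coded or enter the halting count.

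**Step 3: what the recording rule does to the cohort rule.** Let p be the chance that an active subject has a related, asymptomatic laboratory abnormality of Grade 2 or higher by Day 14, and r the share of such events recorded as coded AEs. With q = r × p and 6 active subjects per cohort (Protocol Table 3-1),

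P(at least 2 of 6) = 1 − (1 − q)^6 − 6q(1 − q)^5.

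For p = 0.20 and r = 1: 1 − 0.262144 − 0.393216 = 0.345.

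| p (assumed) | r = 1 | r = 0.5 | r = 0 (literal 8.5) |
|---|---|---|---|
| 0.10 | 0.114 | 0.033 | 0 |
| 0.20 | 0.345 | 0.114 | 0 |
| 0.30 | 0.580 | 0.224 | 0 |
| 0.50 | 0.891 | 0.466 | 0 |

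The documents give no value for p or r. The table also assumes that all six active subjects enrolled under v11.0, that events share one HLGT, and that there are no placebo events. The zeros concern this laboratory count only.

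**The case against.** The strongest reply is that 8.5 only decides where a record is kept. It rules out a separate AE eCRF, its example is about recording a diagnosis instead of its component result, and it speaks elsewhere of grading laboratory AEs. Section 8.6 never names the AE eCRF as its source: the Safety Review Committee (SRC) looks at all safety data for the cohort, and the SDCC reports once the relevant safety data are entered. Grade and relationship are on the laboratory screen. SAP 6.7 reports a decision, taken with DMID, to include related laboratory findings as AEs. Since the laboratory limbs of 8.6 count only related events, that decision covers the right ones.

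This reading is possible, and the SDCC could work that way. But the text does not say so. It still leaves 8.5 stating that isolated abnormalities are not AEs, and it does not explain how a laboratory-form entry would acquire an HLGT. The documents also do not say when the SAP decision took effect or that it governed the Day 14 count.

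A reader might go further and infer that an asymptomatic renal signal cannot stop escalation. The documents do not support that. The SRC reviews laboratory results directly (3.1). The medical monitor or SRC can bring in the SMC with no rule met (3.1, 8.7.2), and 8.6.4 allows suspension for a pattern of laboratory events. The sentinel rule needs an AE but no HLGT, and the SAE limbs do not depend on this recording question.

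A reader might also want to show a zero count with the creatinine grades in Appendices C and D. Those tables apply only to subjects enrolled before v11.0, whose abnormal laboratory results SAP 6.7 says were all AEs. The CTCAE cut-offs used under v11.0 are not in the documents.

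**Conclusion.** The contradiction is real and needs resolving. For subjects enrolled under v11.0, Protocol 8.5, Protocol 8.1.1 and SAP 6.7/15 define three different sets of laboratory AEs, and 8.6 does not say which one it counts. Read literally, 8.5 leaves the laboratory limb of the cohort and study rules with nothing to count for asymptomatic abnormalities of the protocol's own tests; the sentinel rule is affected only to the extent that it also needs an AE. Results linked to signs or symptoms, and CS results of unsolicited panel parameters, still reach the AE eCRF.

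The consequence is loss of a mandatory trigger, not loss of all oversight. Discretionary review remains, but it is weaker: the SRC sees blinded combined data and consists of the medical monitor, a company medical officer and the investigators. The independent SMC has no scheduled data review between its organizational meeting and the final one (8.7.3).

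The conclusion rests on the wording alone. The probabilities under working show how much depends on the recording rule; they do not estimate what happened in the trial.

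**What to change.** Reconcile Protocol 8.1.1, 8.5 and 8.6 with SAP 6.7 and 15:

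1. State in 8.5 and 8.6 whether a graded, related entry on the laboratory form counts as a laboratory AE for the halting rules.
2. If it does, state how it is assigned an HLGT, for example through an SDCC map from each laboratory parameter and direction to a MedDRA term.
3. Use the same AE set for the escalation report and the CSR, and state in SAP 15 whether the decision on related findings applied to escalation decisions.

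No threshold or halting rule is proposed here; which definition applies is for the sponsor to decide.

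The cost is one protocol clarification, a matching SAP edit and, if laboratory-form entries count, one lookup table. Grade and relationship are already collected, so no new data are needed. If entries count, some additional SMC referrals are possible.
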